## **5. Adverse Event Criteria and Reporting Procedures**

This is a small clinical study and so the acting primary investigator will perform continuous monitoring of events. The CGM site and individual patient data will be monitored daily for any patient who is on a CGM monitor. Any protocol deviations and subject withdrawals will be reviewed within 24 hours of occurrence. Aggregate data and enrollment data will be reviewed monthly.

This study has minimal risks, however, in the event of an adverse event secondary to CGM use (such as any significant bleeding, bruising or infection) the acting principal investigator will promptly report the event to the IRB and the medical team. This is a Non-Significant-Risk (NSR) device study and therefore the *Unanticipated Adverse Device Effects* reporting guidelines as per the 21 CFR 812.46 will be followed. Specifically, the study sponsor will immediately conduct an evaluation of any unanticipated adverse device effect. If it is determined that an unanticipated adverse device effect presents an unreasonable risk to subjects all investigations or parts of the investigations presenting that risk will be terminated as soon as possible and no later than 5 working days after the sponsor makes this determination and no later than 15 working days after the sponsor first received notice of the effect. An Unanticipated adverse device effect means any serious adverse effect on health or safety or any life-threatening problem or death caused by, or associated with, a device, if that effect, problem, or death was not previously identified in nature, severity, or degree of incidence in the investigational plan or application, or any other unanticipated serious problem associated with a device that relates to the rights, safety, or welfare of subjects. Because this is a small, pilot study with minimal risk no specific stopping rules will be developed and no interim analysis will be performed.

## **6. Data Management Methods**

We will keep and maintain documentation to verify the consent process, eligibility assessment, protocol compliance, problem/event reporting to the IRB, quality control as well as all data collection. This is a non-significant risk (NSR) study and the study PI, [name], will be the sponsor. Maintenance of records and reporting obligations by the sponsor and investigators as per Part 812 of the Investigational Device Exemption will be followed. These records will include name and intended use of the device, objectives of the investigation, explanation of why the device is not a significant risk device, name and address of investigators and IRB, description of good manufacturing practices followed, subject case history, device receipt, use or disposition history, all correspondence, the protocol and documentation of protocol deviations as well as any other records and reports required by the FDA. All hardcopies will be maintained in a locked office while electronic data will be saved on an access controlled network drive. To ensure data safety and reliability, server back-up procedures are executed daily to back up all electronic study-related materials, which include the database, Word® documents, statistical programs, and files. Access to the data requires user authentication. Authorized users include only research team members.

## 7. Quality Control Method

We will use checklists to verify that every subject has undergone appropriate consent, eligibility screening and safety monitoring during the study. Appropriate CGM placement and function will be performed daily on all enrolled subjects. Glucose data from CGM monitors will be compared to sampled blood glucose levels to assess for accuracy of the CGMs. We will also maintain a log of any protocol deviations and reportable events.

Criteria for early termination of study participation:

- Development of widespread skin disease such that placement of a CGM sensor would be difficult to secure
- Development of infection or colonization with multi-drug resistant organisms (i.e. MRSA, VRE, ESBL producing bacteria)
- Development of significant erythema, induration, infection or other adverse event at the CGM insertion site
- Study cancellation by the sponsor.
- Participant/family failure to follow the study requirements.
- The Principal Investigator judges it is in the best interest for the child to be taken off the study.
- Parent withdraws permission for the child to participate in the study.

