management decisions will be made by the clinical team based on laboratory or bedside monitor-confirmed blood glucose values. The CGMs will be calibrated, at a minimum, every 12 hours with a blood glucose value measured by bedside glucometer. Additional calibrations will be performed if more frequent blood glucose monitoring is deemed necessary by the NICU team. In the “Standard of Care” group, the only change to current management is the potential performance of additional blood glucose checks that may be prompted if repeated unrecognized severe hypoglycemia is detected by the research team. The CGM will remain in place until the infant is no longer being monitored for glycemic stability or until the infant is discharged. If hypoglycemia work-up and management lasts longer than a week, the CGM sensor will be replaced on the seventh day after initial insertion. In the case of a sensor dislodgement or malfunction, it would also be replaced. Lastly, if a patient continues to have unstable hypoglycemia for longer than 28 days (eg. four 7-day cycles of CGM) then their study participation will also end at that time.

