#### ***Description of Study Treatments or Exposures/Predictors***

Continuous Glucose Monitors (CGMs) will be placed in all enrolled patients. CGMs measure glucose concentration in the interstitial fluid of the subcutaneous space every few seconds and report average blood glucose levels approximately every 5 minutes. CGMs have 3 components: a glucose sensor, a transmitter, and a receiver. The glucose sensor is inserted subcutaneously with a 26-gauge introducer needle and remains in place under the surface of the skin for up to 7 days. The sensor’s platinum tip is embedded with glucose oxidase enzyme, which catalyzed a reaction whereby electrical current is generated which is proportional to ambient glucose concentration. The current is then measured and translated into a glucose reading once it is wirelessly sent by the transmitter to the small hand-held receiver. The receiver then displays the glucose level in mg/dL and can alert at specified glucose levels.

*c. Definition of Primary and Secondary Outcomes*

This is a pilot study to determine the feasibility of using CGMs to improve short term outcomes of neonates with hypoglycemia. Planned comparisons for a larger study will be powered from the data obtained. The primary endpoint will be a reduction in incidence and severity of hypoglycemia in infants on the CGM Protocol. Secondary outcomes will include reduction in in time-to-diagnosis, time-to-treatment initiation and time-to-euglycemia on a sustainable feeding regimen.

*d. Data Collection Methods, Assessments and Interventions*

- *Data collection:*

When a subject is first enrolled we will collect demographic Information (age at diagnosis of hypoglycemia, gestational age at birth, sex) as well as physical characteristics (weight and body surface area). Once a subject is on a CGM, the CGM glucose data will be downloaded onto a research team computer and reviewed daily. Laboratory results (including blood glucose levels and critical sample results (ketones, insulin, cortisol, growth hormone, fatty acids, total and free carnitine, plasma amino acids, urine organic acids, lactic acid, pyruvate), brain imaging and EEG readings, all intravenous and enteral sources of glucose, other sources of nutrition, hypoglycemia therapeutic interventions (eg. glucagon, diazoxide, octreotide, corticosteroids and carnitine replacement) as well as underlying etiology of hypoglycemia and other associated diagnoses will be reviewed and collected every 2-3 days.

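### Section 7 ends study participation, not only sensor wear, for site reaction, unsecurable sensor, resistant organisms and non-adherence, and nothing keeps these infants in chart follow-up or in the analysis

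*Combined protocol and SAP*

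**What the plan says.** Section 7 (Quality Control Method) has a list titled "Criteria for early termination of study participation". Four of its entries concern the device, infection control or adherence:

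- "Development of significant erythema, induration, infection or other adverse event at the CGM insertion site"
- "Development of widespread skin disease such that placement of a CGM sensor would be difficult to secure"
- infection or colonization with multi-drug resistant organisms
- "Participant/family failure to follow the study requirements"

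The list also contains "Parent withdraws permission for the child to participate in the study", cancellation by the sponsor, and a judgement by the principal investigator. All entries lead to the same result. There is no status in which the sensor is off but the infant is still followed.

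One kind of device failure is handled differently. Section 4a says: "In the case of a sensor dislodgement or malfunction, it would also be replaced". Section 4d agrees.

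Section 4d describes periodic collection of laboratory results, nutrition and glucose sources, and treatments. It closes with "underlying etiology of hypoglycemia and other associated diagnoses will be reviewed and collected every 2-3 days". Section 8 defines hypoglycemia by a blood value below the age threshold, or by sensor values below threshold for more than 30 minutes when no blood value was taken. It names no analysis population and no rule for missing or incomplete follow-up. Section 5 says only that withdrawals are reviewed within 24 hours.

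**The concern.** The listed events happen after randomization. If they end participation, they may also end the recording of outcomes that a chart review would still supply.

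The infants affected may not be a random subset. Sensor wear continues until glycemic stability, discharge or day 28, with a new sensor every seven days. An infant with a long course therefore has more time in which a site reaction, colonization or non-adherence can occur. That infant also tends to have the largest time to euglycemia. Losing such infants would make the observed courses look shorter and less variable than they are. This matters for a pilot whose stated statistical purpose (Section 9) is to supply a variance for a larger trial.

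An intention to analyze as randomized would not repair this, because data that were never collected cannot be analyzed later.

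**Working it through.** **Step 1: which outcomes need the sensor?** Sections 4c, 4d and 8 side by side:

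| Outcome | Source | Obtainable after sensor removal? |
|---|---|---|
| Hypoglycemia by blood value | laboratory or bedside meter | yes |
| Hypoglycemia by sensor only (>30 minutes, no blood value) | CGM | no |
| Time to diagnosis | work-up and etiology in the chart | yes |
| Time to treatment initiation | treatments in the chart | yes |
| Time to euglycemia on a sustainable regimen | blood glucose and feeding records | yes |

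Only one limb of the primary outcome depends on the device.

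**Step 2: does any section retain the infant?** Sections 4a, 4d, 4e, 5, 7, 8 and 9 contain no statement that chart collection continues after termination, and none that it stops. At day 28, Section 4e ends participation and sensor wear together.

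**Step 3: is there a plan figure to reproduce?** No. Ten per arm rests on convention for pilot studies (Section 9). No error rate, power, effect size, SD or dropout rate is given.

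**Step 4: how likely is at least one termination?** The per-infant probability p is an assumption, so a range is shown. With 20 infants, P(at least one) = 1 − (1 − p)^20, and the expected number is 20p.

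| Assumed p | Calculation | P(at least one) | Expected number |
|---|---|---|---|
| 5% | 1 − 0.95^20 | 64% | 1 |
| 10% | 1 − 0.90^20 | 88% | 2 |
| 20% | 1 − 0.80^20 | 99% | 4 |

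**Step 5: what does a loss cost?** One infant is 1/10 = 10% of an arm. Suppose incidence means the proportion of infants with an event, and an infant is terminated with none recorded. Treating that infant as event or non-event moves the arm's incidence by 10 percentage points. One such infant in each arm gives best-to-worst bounds on the difference that are 20 points wide. Two in each arm give 40 points.

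For precision, in SD units, the 95% half-width of a mean difference is t(0.975; 2n − 2) × √(2/n). The 95% limits for a pooled SD are the estimate times √(df/χ²), with df = 2n − 2.

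| n per arm | Half-width | Pooled SD multipliers |
|---|---|---|
| 10 | 0.94 | 0.76 to 1.48 |
| 9 | 1.00 | 0.75 to 1.52 |
| 8 | 1.07 | 0.73 to 1.58 |
| 7 | 1.17 | 0.72 to 1.65 |

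The loss of precision is modest. Selective loss is the more serious issue, and these figures do not measure it.

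**The case against.** The strongest reply is that the plan is silent on this and makes no rule that discards data. Section 7 does not mention data collection, and the chart review in Section 4d is not tied to sensor wear. The consent form was not available here and may cover use of records after termination. This stands as a limit on the wording: no text expressly stops chart collection. It does not remove the point, because ending participation is most naturally read as ending collection, and staff could apply it either way.

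Termination may also be rare. Section 3 reports no injuries, serious bleeding or infections in close to 1,000 children under 36 months, and Section 2 reports no significant complications under 3 years. Those populations differ from this one, and the reports do not cover colonization or non-adherence. They do show that 20% should not be read as a forecast. In addition, an infant who already has a diagnosis at termination has a complete time to diagnosis.

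A reader might infer three stronger claims that the documents do not support:

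- **Any device problem costs data.** It does not: dislodgement and malfunction lead to replacement.
- **The arm comparison is biased in a known direction.** Every infant wears the same sensor, so there is no evident reason for site reactions to differ with alarm status. Calibration and blood checks fall to NICU staff, so a difference in family adherence is speculation.
- **The bias has a known size.** If the one or two highest of ten normal values are lost from one arm, its mean shifts by 1.539/9 = 0.17 SD or (1.539 + 1.001)/8 = 0.32 SD. That is a worst case for means, whereas Section 8 uses the Mann-Whitney test for the times. It is also small beside the 0.94 SD half-width at full enrollment.

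**Conclusion.** The point holds as a design weakness that can be avoided. Four reasons that do not by themselves limit access to the chart end participation in the same way as withdrawn permission, and nothing retains the infant in follow-up or in the analysis.

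The termination probabilities in Step 4 rest entirely on assumed rates and on independence between infants. That loss would be selective is plausible from the exposure argument, but the documents do not demonstrate it. No size or direction of bias between arms can be given. In an unpowered pilot of 20 the change is worth making because it is inexpensive, and because the omission cannot be repaired once the data have gone uncollected.

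**What to change.** - **Section 7:** define two statuses, *sensor discontinued* and *study discontinued*. Leave the criteria for removing a sensor unchanged. Reserve study discontinuation for withdrawal of parental permission or cancellation of the study.
- **Sections 4d and 4e:** state that the existing chart collection continues after sensor discontinuation to the planned end of follow-up (resolution, discharge or day 28).
- **Section 8:** analyze every infant in the arm to which it was randomized. Use blood-glucose-defined events over full follow-up. Count sensor-only events only over sensor-wear time, for example as a rate per sensor-day, so that the change in ascertainment at removal is not mistaken for fewer events. Report the number of infants, the reason and the day of sensor discontinuation by arm.

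The cost is a few sentences of protocol text and some further chart reviews for each infant who stops, on the schedule already in place. Sensor-only events after removal remain unobservable. Blood-defined events still depend on how often blood is sampled, which alarms can raise in the CGM Protocol arm while the sensor is on; this change does not address that.

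Replacing losses by enrolling more infants is a weaker alternative. It would take 10/0.9 = 11.1, so 12 per arm at 10% loss, or 10/0.8 = 12.5, so 13 per arm at 20%, and it would not remove selective loss.

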## 8. Data Analysis Plan

Hypoglycemia will be defined as a laboratory or bedside monitor blood glucose value of <50 mg/dL prior to 48 hours of life and <70 mg/dL after 48 hours of life or CGM values below threshold for >30 minutes with no concomitant blood sugar reading. Hypoglycemic episodes within one hour of each other will be considered as one event. Severe hypoglycemia will be defined as less than 40mg/dL. Euglycemia will be defined as 48 hours with blood glucose equal or greater than 70mg/dL after 48 hours of life or equal or greater than 50mg/dL if before 48 hours of life.

We will record all blood glucose levels, laboratory data related to the investigation of the underlying cause of hypoglycemia, intravenous and enteral sources of glucose, and other related therapeutic interventions such as administration of diazoxide, octreotide, glucocorticoids, and carnitine. Data analysis will begin by comparing blood glucose data with information from the CGM monitors to assess for accuracy of the CGMs. This will be done by calculating the mean-absolute-relative-difference (MARD) between sensor-measured glucose levels and laboratory or bedside meter-measured blood glucose values. We will then compare the severity and frequency of hypoglycemia, as well as the time to diagnosis and time to euglycemia on a sustainable feeding regimen between the “CGM Protocol” and “Standard of Care” groups. Chi-squared analysis will be used to assess differences in the incidence of hypoglycemia while the Mann-Whitney U test will be used to analyze differences in time-to-diagnosis and time-to-euglycemia.

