### 4. Design and Methods

#### a. Study Design

We aim to carry out a prospective, randomized clinical study examining the efficacy of continuous glucose monitoring in neonates with hypoglycemia. Eligible infants will be late preterm and term infants admitted to the Boston Children's Hospital NICU, who have had two documented hypoglycemic episodes during their admission. Hypoglycemia will be defined depending on age: <50 mg/dL prior to 48 hours of life and <70 mg/dL after 48 hours of life.

The research team will review the glucose levels for patients admitted to the NICU daily in order to identify those with hypoglycemia. Screening will be conducted by study staff through the electronic medical record system; supplemental screening will be provided daily through BCH360. After obtaining permission and an introduction from the patient's NICU staff, a member of the research team will contact the family to obtain consent. The goal will be for patients to be recruited within 24 hours after criteria for hypoglycemia have been met.

All enrolled infants will be placed on a CGM monitor (Dexcom G4 Platinum Pediatric Continuous Glucose Monitoring System). The CGM sensor will be inserted subcutaneously in the lateral thigh by a trained study team member. Prior to study commencement, as well as actively throughout the study duration, the research team will review the proper use of CGMs with the NICU staff (most importantly, how to calibrate the sensor with glucose levels from blood sampling). The NICU staff will also be trained to avoid using sensor values to guide treatment directly, as it is only a monitoring device. All concerning CGM glucose readings must be confirmed by blood glucose sampling.

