Infants will be randomized to a "CGM Protocol" or a "Standard of Care" group. We aim to enroll ten patients in each study arm. Those on the CGM Protocol will have a fully accessible CGM that will be analyzed in real-time for blood glucose trends and will alarm for any blood glucose level approaching hypoglycemic threshold. The CGM alarm will sound if blood glucose is less than 60 mg/dL for all patients. The CGM will also alarm if the rate of drop in blood glucose is greater than 20 mg/dL/minute and thus concerning for impending hypoglycemia. These thresholds are programmed into the CGM by a study team member and will not be modifiable by the medical team. Those in the "Standard of Care" group will have a CGM in place but live readings will not be available to the clinical team. However, the research team will review CGM data from the "Standard of Care" group daily and if a subject in the "Standard of Care" group has three episodes of unrecognized severe hypoglycemia (eg. BG <40 mg/dL), the study team will alert the NICU providers. Notification will occur immediately following identification of the third unrecognized severe episode of hypoglycemia, which will at most be 24 hours after the event occurred.

For subjects in the "CGM Protocol" group, whenever the CGM alarms or there is a concerning blood glucose trend according to the CGM, the nurse will be asked to check a blood glucose value. All clinical

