- *Assessments:*

The CGM site will be evaluated daily to assess for any signs of bleeding or infection. CGM readings will be downloaded to a study team computer once a day. The CGM data will be reviewed daily to ensure the CGM monitor is functioning properly, being calibrated appropriately and to assess whether any episodes of severe unrecognized hypoglycemia have occurred.

- *Interventions:*

Subjects in the study will have a continuous glucose monitor (CGM) placed in one of their thighs. A numbing cream will be used before the CGM is inserted to reduce pain. The CGM has a small plastic catheter with a needle in it. It comes with an insertion device which pushes the catheter under the skin. The needle is then removed, so only the catheter stays under the skin with the device on top of it. After the CGM is placed, two blood glucose levels will be obtained (usually by heel prick) so that the device can be calibrated. Afterwards at least two blood sugar levels need to be obtained every day so that the CGM can continue to work properly. Infants with hypoglycemia need to have their blood glucose monitored routinely, so on most days no extra blood glucose sampling will be required as we will use the values obtained by the NICU team. Additional blood glucose levels may need to be obtained if the CGM reports current or impending hypoglycemia. All non-CGM monitoring and management decisions will be at the discretion of the NICU team. The CGM may need to be replaced in case of a sensor dislodgement or malfunction, or if it has been in place for more than 7 days. Live CGM glucose values will be available to the medical team in the “CGM protocol” group. Additionally the medical team will be provided print outs of the CGM data on a daily basis for the “CGM protocol” group. CGM data from patients in the “Standard of Care” group will also be reviewed daily. Notification will occur immediately following identification of three unrecognized severe episodes of hypoglycemia. Given that the CGM data will be analyzed daily, this will at most be 24 hours (although most likely less than 24 hours) after the event occurred.

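### The Section 8 event rule depends on whether blood was drawn, and the unmasked CGM raises blood sampling in one arm only, so event frequency and severity can differ between arms with identical glucose

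*Combined protocol and SAP*

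**What the plan says.** Section 8 gives two routes to an event. The blood route needs one laboratory or bedside value below the age-specific threshold (50 mg/dL before 48 hours of life, 70 mg/dL after), with no minimum duration. The sensor route is "or CGM values below threshold for >30 minutes with no concomitant blood sugar reading". Episodes within an hour of each other are merged. A concomitant reading is not defined. Severe hypoglycemia is below 40 mg/dL, with no source or duration given.

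Blood sampling differs by arm. In the CGM Protocol group (Section 4a), "whenever the CGM alarms or there is a concerning blood glucose trend according to the CGM, the nurse will be asked to check" a blood value, and "The CGM alarm will sound if blood glucose is less than 60 mg/dL for all patients". In context this describes the unmasked group at any age. Section 4a adds that "All concerning CGM glucose readings must be confirmed by blood glucose sampling". Section 4d says that "Live CGM glucose values will be available to the medical team" in that group and that "Additional blood glucose levels may need to be obtained if the CGM reports current or impending hypoglycemia". Standard of Care infants "will have a CGM in place but live readings will not be available to the clinical team". Study-prompted checks can follow there only after the research team finds three unrecognized severe episodes.

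Section 4c makes reduced incidence and severity the primary endpoint. Section 8 compares severity and frequency between arms and names a chi-squared test for incidence. Section 9 intends the variance of frequency and severity for planning a larger study.

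**The concern.** An outcome compared between randomized arms should be ascertained alike in both. Here the intervention changes how often blood is drawn, and drawing blood changes which lows count. Two groups with the same glucose could yield different event counts, and a real difference could be masked or exaggerated. A larger sample would not remove this.

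At stake are the between-arm comparison of frequency and severity, and the planning inputs for the larger trial. Section 1 also says that the pilot is meant to test whether its outcome measures are valid, so a measure that shifts with sampling intensity bears directly on its purpose.

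**Working it through.** The plan states no event rate or effect size, so there is no figure to reproduce. The check applies the Section 8 rule first by hand and then by simulation.

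**By hand: same glucose, with and without a prompted check**

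| Case | No prompted check | Prompted check |
|---|---|---|
| 1. True 20-minute dip, no routine draw | 0 (sensor run too short) | 1 (low blood value) |
| 2. False 45-minute sensor low, true glucose above threshold, no routine draw | 1 (sensor run, no blood) | 0 (blood not low) |
| 3. True sustained low during which one routine blood value is not low | 0 (sensor route closed) | 1 if a further check reads low |
| 4. True low of more than 30 minutes, sensor and blood agree | 1 | 1 |

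Cases 1 and 3 raise the CGM Protocol count relative to Standard of Care. Case 2 lowers it. Case 4 is neutral. The text alone shows that counts can differ, but not which effect prevails.

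**By simulation: size under assumed inputs**

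The same 7-day glucose and sensor traces were scored twice by Section 8: with routine checks only (Standard of Care), and with routine plus prompted checks (CGM Protocol). No treatment effect was included, so the true ratio is 1.

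- From the documents: the 70 mg/dL threshold, the 60 mg/dL alarm, the more-than-30-minute rule, one-hour merging and 12-hourly calibration.
- Assumed: mean glucose 80 to 100 mg/dL; within-infant SD 12 or 18; autocorrelation time 40 or 90 minutes; sensor MARD 5 to 20%; meter CV 5%; routine checks every 3, 6 or 12 hours; a prompted check 10 minutes after the alarm; concomitant taken as any blood value during the sensor run.

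Ratio = events per day in CGM Protocol ÷ events per day in Standard of Care.

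- Over 144 scenarios the median was 1.15 (interquartile range 1.01 to 1.25, range 0.46 to 1.72).
- The ratio of between-infant variances of the counts had median 1.56 (0.66 to 4.25). Section 9 would pass this variance on.
- Infants with any event: median 0.99 in Standard of Care and 0.98 in CGM Protocol. The median absolute difference was 0.007 and the largest 0.20.

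A second simulation on different assumptions (base case: 3-hourly routine checks, 56 v 89 draws per infant) gave 18.0 v 21.3 events, and 21.3 ÷ 18.0 = 1.18. The ratio was 1.41 with fast dips and 0.90 with rare lows. It was 0.14 in an extreme case, with a sensor reading 15% low, 20% noise and rare true lows.

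**Severity (same base case, Standard of Care v CGM Protocol)**

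- If any undrawn CGM value below 40 counts: 0.79 v 0.46 severe events per infant, ratio 0.46 ÷ 0.79 = 0.58.
- If the CGM must stay below 40 for more than 30 minutes: 0.13 v 0.45, ratio 0.45 ÷ 0.13 = 3.5.
- Infants with any severe event: 0.43 v 0.28 under the first rule and 0.10 v 0.27 under the second.

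The direction reverses with a choice that the plan leaves open.

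**Is a CGM-only count neutral?**

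With identical sensor traces it is, by construction: 14.68 events per infant in both arms, ratio 1.00. That requires equal calibration. Section 4a sets a 12-hourly minimum and allows more calibrations when the NICU team wants closer monitoring, so prompted values might be entered in one arm only. Under that assumption (96 scenarios), the null CGM-only ratio was 0.80 (0.32 to 0.99), against 1.00 (0.29 to 1.67) for the Section 8 rule. MARD alone would not reveal it. At nominal 10%, MARD on routine pairs was 11.4% v 11.3%, while the mean signed sensor-minus-blood difference was +1.0% v +4.6%.

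**The case against.** The strongest reply is that giving blood precedence is coherent. Care rests on blood values, concerning sensor readings must be confirmed, and Section 8 lets blood overrule a less accurate device. A CGM-only count keeps lows that blood disproved and drops blood-confirmed dips of 30 minutes or less. That is a fair case for keeping the hybrid count, but it does not make that count comparable between arms.

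It can also be said that the pilot is unpowered and that its noise exceeds the bias. With 10 per arm and an assumed count CV of 0.5 to 1.0, the 95% limits on a rate ratio span a factor of exp(1.96 × CV × √(2/10)), or 1.55 to 2.4, each way. This stands for the pilot's own conclusions. It does not help the inputs carried forward. Retained traces would allow later rescoring, but a rule chosen then would not be prespecified.

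A reader might infer that closer looking must count against the CGM arm. The documents do not support this, because cancelled false lows act the other way. A reader might also infer that the CGM-only count should simply replace the hybrid. That is not supported either: if prompted values recalibrate one arm only, the CGM-only count falsely favours the device. With that calibration and an assumed glucose response together, the median true ratio was 0.73, the Section 8 rule gave 0.97 and the CGM-only count 0.53. The CGM-only count was closer to the truth in only 54 of 96 scenarios.

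Nor does the point condemn the chi-squared test if incidence means any event per infant. Entry requires two earlier episodes, so that measure is nearly saturated. Per-infant severe hypoglycemia is not equally protected.

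**Conclusion.** The concern holds for event frequency and severity and should be fixed. The mechanism follows from Section 8 read with Sections 4a and 4d and needs no assumption about glucose. Its size and sign are not determined by the documents. The null ratio of about 1.15 (roughly 0.5 to 1.7) is illustrative: it rests on assumed glucose variability, sensor and meter error, routine sampling and alarm response, and on one reading of concomitant. It covers checks prompted by sensor values below 60 only. Checks prompted by trends or live values would add to the sampling difference by an amount that the documents do not give.

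**What to change.** In Section 8:

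- Prespecify a CGM-only count by one rule in both arms: episodes below the age-specific threshold for more than 30 minutes, per monitored CGM day, regardless of blood draws, merged by the existing one-hour rule. Apply the same rule below 40 mg/dL for severity.
- Report it beside the hybrid and blood-confirmed counts, both for the comparison of frequency and severity and for planning inputs. Do not rely on the hybrid count alone.
- Define a concomitant reading, and state the glucose source of a severe value.
- Report by arm: blood checks per day, calibrations per day, and MARD and mean signed sensor-minus-blood difference, the last two on routine (not prompted) pairs.

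In Section 4a, state whether prompted blood values are entered as calibrations, by the same rule in both arms. Give the CGM-only count priority only if calibration is the same in both.

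The cost is wording in Section 8, one sentence in Section 4a and one by-arm table. The sensor data exist for every infant, since "CGM readings will be downloaded to a study team computer once a day", and Section 8 already records all blood values. A mark showing which checks were prompted may be needed to separate routine pairs. The downside is that the CGM-only count carries sensor error and can falsely favour the CGM arm if calibration differs, so it must be read with the signed difference and the other two counts.
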